#### 9.4.2 ANALYSIS OF THE PRIMARY EFFICACY ENDPOINT(S)

The primary endpoint is the average of AF burden at the end of the first week.

We will use Mobile Cardiac Telemetry to determine AF burden before surgery (eligibility visit), for two weeks during ScNS, 3 weeks following surgery and 3 months following surgery.

The average of AF burden at the end of the first week will be calculated per patient as the time spent in AF during the first week divided by the total time a patient is under observation during the first week. Change of the average AF burden from the baseline will be computed for each patient. The change in the average AF burden will be compared between group A (experimental) and group B (control) using the Wilcoxon rank sum test at a two-sided significance level of 0.025.

*The following secondary analyses of the primary endpoint will be performed:*

- 1) We will compare the baseline AF burden and the baseline number of Apple watch-detected AF episodes between groups. The number of Apple watch-detected AF will be standardized by the number of days that a subject is under observation in the respective time period. Further we will compare reduction in AF burden from baseline at weeks 1, 2, 3 and 12 in both Group A and Group B to test the null hypothesis that there is no reduction of AF burden in the two groups and between the two groups. We will also compare the reduction in the number of Apple watch-detected AF episodes from the baseline in the period between week-3 and the end of study in both Group A and Group B to test the null hypothesis that there is no difference in detected AF episodes in the two groups and between the two groups. Linear mixed effect models will be used for the comparisons, with Group, Week and Group by Week interaction as fixed effects, and a random intercept per subject. Week will be coded first as a categorical variable, and appropriate contrasts will be set up for the temporal comparisons. If outcome variables appear to be linear in time, we may model Week as a continuous fixed effect.
- 2) We may also compute the difference-in-difference statistics for the treatment for the 4 time intervals of the treatment, baseline and t weeks 1, 2, 3 and 12.

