We will compare the number of Apple watch-detected AF episodes between week-3 and the end of study between Group A and Group B to test the null hypothesis that there are no differences in detected AF episodes between the two groups. For each patient, we will record the number of days that the patient is under observation, and the number of days that AF episodes are detected. Assuming that each patient's data follows a binomial distribution and the probability of AF daily detection is the same within group. Since patients' data are independent from each other and the sum of independent binomials are still a binomial, we can compare the two groups as two binomials with potentially different rates of AF detections. Fisher's exact test will be performed for this comparison at a two-sided significance level of 0.05.

The overall scores of Quality of life (AFEQT-AF, EQ-5Q-5L) questionnaires will be compared at the following time points, baseline, 3 week and 3 month visits by the same linear mixed effect models as described for aSKNA. The same missing data treatment as stated above will be employed in the linear mixed model analyses of these two outcomes. Item and total scores may be transformed if deemed necessary to fulfil model assumptions.

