8	6-22-2022	
 
1. Addition of Adverse Events
 
2. Addressing Inconclusive ECGs from Apple Watch
 
3. Apple Watch Monitoring and Timeline
 
	
Based on patient reported adverse events and past literature, goosebumps and hot flashes are known to have association with spinal cord stimulation. We are adding them as potential adverse events.
 
In the event that the subject does not want to wear the research Apple devices for Apple Watch Monitoring, we want to provide an option of allowing them to continue the monitoring between Week 3 and Month 3 procedures. Apple Watch Monitoring will allow the Principal Investigator and research staff to know when the patient is having AF determined by the Apple Watch detection.
 
To account for Apple watch ECG readings that result as Inconclusive.
 
We found that Apple Watch is effective in detecting AF after randomization. However, because we do not have data before randomization, there are no baseline AF data to compare with. Therefore, we request the permission to give the patient an Apple Watch and iPhone during baseline visit. The patient will wear the watch before randomization to collect baseline information. We also revised the statistical analysis. These changes do not affect the primary outcomes of the study.

9	9-28-2022	
 
1. Inclusion criteria – expand to use of clinical ePatch recordings for AF burden
 
	Most of the patients with atrial fibrillation (AF) had AF burden determined clinically by ePatch recordings. If the ePatch

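### Sections 9.4.2 and 9.4.3 test nearly the same Apple Watch comparison on two different outcomes with no stated precedence, and the 9.4.3 version leaves out the baseline watch period

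*Combined protocol and SAP*

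**What the plan says.** **Section 9.4.2, first secondary analysis of the primary endpoint.** Watch-detected AF is to be "standardized by the number of days that a subject is under observation in the respective time period". The quantity compared is the "reduction in the number of Apple watch-detected AF episodes from the baseline in the period between week-3 and the end of study". The null is that "there is no difference in detected AF episodes in the two groups and between the two groups", so it covers change within each group as well as the contrast between them. On method: "Linear mixed effect models will be used for the comparisons, with Group, Week and Group by Week interaction as fixed effects", with a random intercept per subject. No significance level is attached to the watch outcome.

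**Section 9.4.3, under the SKNA and QOL analyses.** The paragraph opens with the number of watch-detected episodes, in the same window, "to test the null hypothesis that there are no differences in detected AF episodes between the two groups". It then records, for each patient, "the number of days that the patient is under observation, and the number of days that AF episodes are detected". These day counts are summed within each group, treated as two binomials and compared by Fisher's exact test at two-sided 0.05. There is no baseline term.

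**Baseline watch data.** The Schedule of Activities (1.3) and the Apple Watch paragraphs of 8.1 have patients wear the watch from the Baseline visit. The amendment history (10.4, version 8) gives the reason: "The patient will wear the watch before randomization to collect baseline information".

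**Crossover.** Under 6.3, Group B is unblinded three weeks after the procedure and offered active stimulation. The watch window opens at that same point.

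**The concern.** One between-group question has two planned answers. They differ in the unit counted (episodes or days), in the use of baseline (change from it, or none) and in the test. If they disagree, the plan does not say which one counts, and the choice would be made after both results are known.

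The missing baseline in 9.4.3 matters in its own right. Patients with paroxysmal AF differ widely in episode rate and the arms are small. A chance difference between arms before stimulation therefore passes straight into a comparison made on follow-up alone, although the data to correct for it are already recorded.

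**Working it through.** **1. The two analyses side by side**

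| | 9.4.2 | 9.4.3 |
|---|---|---|
| Unit | Episodes per observed day | Days with any AF out of days observed |
| Window | Week 3 to end of study | Same |
| Baseline | Change from it | None |
| Level of analysis | Patient (mixed model) | Patient-days pooled by group |
| Null | Within and between groups | Between groups |
| Stated level | None for this outcome | Two-sided 0.05 |

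**2. Design size.** The documents give no sample size or power for either watch analysis. The primary calculation in 9.2 reproduces: effect size (76.3 - 5)/44.8 = 1.59; a simulated Wilcoxon test at 0.025 gives 79% power with 9 per arm and 84% with 10; 10/0.70 = 14.3, rounded up to 15. The range used below is therefore 10 (after the planned 70% retention) to 15 per arm.

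**3. Can the two conflict?** Simulated with 10 per arm, tests at two-sided 0.05 and no crossover. Assumed, not in the documents: 14 baseline and 63 follow-up days, nominal between-patient ICC 0.2.

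- *Unequal baseline.* Group A goes from AF on 80% of days with 5 episodes per AF-day to 60% with 3. Group B stays at 40% with 3. Episodes per day: A 0.80 x 5 = 4.0 falling to 0.60 x 3 = 1.8, a change of -2.2; B 1.2 throughout, a change of 0. Follow-up AF-days: A 60%, B 40%. The 9.4.2 change favours A in 100% of runs, and the 9.4.3 Fisher test significantly favours B in 98%. Per-patient AF-days taken as change from baseline favours A in 94%, so the reversal comes from the missing baseline.
- *Fewer episodes on the same days.* AF on 50% of days throughout; A goes from 5 to 2 episodes per AF-day, B stays at 5. Episodes per day: A 2.5 to 1.0, B 2.5 to 2.5. The 9.4.2 change is significant for A in 96% of runs. Per-patient change in AF-days is significant in about 5% (2.2% + 2.7%). Here the definition alone decides the answer.

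**4. How large can chance imbalance be?** Section 9.2 quotes quartiles of 0.31, 1.21 and 4.99 episodes per day from ECG-patch monitoring. Fitting a log-normal gives SD of log rate = ln(4.99/0.31)/(2 x 0.6745) = 2.06. The standard error of the arm difference in mean log rate is 2.06 x sqrt(2/n): 0.92 with 10 per arm and 0.75 with 15. A one-standard-error imbalance is thus a ratio of about e^0.92 = 2.5 or e^0.75 = 2.1 in typical episode rate.

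**5. What baseline adjustment is worth.** Assumptions: those rates, over-dispersed daily counts, 14 baseline and 70 follow-up days, within-patient SD of log rate between periods 0.3 to 0.7, a true 75% reduction, 10 to 15 per arm, two-sided 0.05.

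| Analysis | Power, no crossover |
|---|---|
| Change in episodes per day (9.4.2) | about 8-25% |
| Per-patient AF-days, no baseline | about 23-39% |
| Per-patient AF-days, baseline-adjusted | 58-98% |
| Log episodes per day, baseline-adjusted | 73-100% |

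Suppose 70% of Group B cross over, with effect from two weeks into the window, and their later data stay in. The baseline-adjusted AF-day figure then falls to about 17-32%.

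**6. The pooled Fisher test as written.** It treats days within a patient as independent. With no treatment effect it rejects in about 67-78% of runs under the step 5 assumptions. In a separate run with 10 per arm and 63 days, its type I error was 4% at ICC 0, 30% at 0.05 and 66% at 0.33. Under the 75% reduction it rejects in 88-93%.

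**The case against.** *The nulls are not identical.* Correct: 9.4.2 also tests change within groups. The between-group part is still duplicated.

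*A reader might infer that both planned analyses waste most of the available power.* That does not hold for 9.4.3. Its pooled test rejects often whether or not there is an effect, so its fault is false positives. The 23-39% above belongs to a per-patient test without baseline, which the plan does not propose. It is shown only to isolate the value of the baseline.

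*A reader might infer that AF-days is the better measure and episodes per day the mistake.* The documents do not rank them. AF-days cannot tell one episode from many on a day. Episode counts depend partly on ECGs that participants start at their own option (8.1). Baseline-adjusted log episodes per day did at least as well as AF-days in the illustration.

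*The inputs are not watch data.* True: the quartiles come from continuous patch monitoring. Thinning the rates to 10-30% left the ordering of methods unchanged, so this limits the figures rather than the ranking.

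*The plan has safeguards.* Section 9.4.1 promises model diagnostics and 9.4.2 allows GEE. These could repair a poorly fitting mixed model, but they neither choose an outcome nor give 9.4.3 a baseline.

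*Leaving out baseline may be deliberate.* Patients enrolled before version 8 may have no watch baseline. That is a fair reason not to require one, and a model can keep those patients while using baseline for the rest.

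*The stakes are low.* This stands. Watch-detected AF is in no endpoint list or numbered hypothesis, and 9.4.3 reports nominal p-values unless it says otherwise.

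**Conclusion.** The point holds as a gap in specification. Two outcomes and two tests serve nearly the same between-group null over the same window with no precedence, and one of them omits a baseline that the trial collects. The text alone shows this. The simulations show that the conflict can be real, up to significant results in opposite directions in a case built with a large baseline imbalance.

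The gain from adjusting for baseline (about 23-39% to 58-98% for per-patient AF-days) rests on the assumed rates, period lengths and 75% effect, and on no crossover. Crossover uptake is not in the documents; with 70% uptake left unhandled, most of the gain goes. Baseline adjustment and a crossover rule are therefore needed together.

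The change should be made but is not critical: these are supportive analyses, and the primary week-1 AF burden comparison is unaffected.

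**What to change.** Before unblinded analysis, amend 9.4.2 and 9.4.3 to:

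1. Name one watch outcome for week 3 to end of study. Either measure is defensible; choose one and give the reason.
2. Name one patient-level analysis as governing, adjusted for the same measure in the baseline watch period. Examples are ANCOVA on each patient's proportion of AF-days, or ANCOVA on log episodes per day with a stated rule for zeros. Fix a single method so that no choice remains at analysis.
3. Keep patients with no watch baseline, for example by modelling baseline as a response.
4. Separate Group B watch data after crossover from the between-arm comparison, and report them with the crossover analysis.
5. Label the other measure descriptive and drop its separate significance test. If AF-days is chosen, replace the pooled Fisher test as well.

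The cost is SAP wording; both watch periods are already recorded. Step 4 shortens Group B follow-up for those who cross over, so the between-arm comparison will be less precise than the no-crossover figures suggest, and the report should say so.

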#### 9.4.3 ANALYSIS OF THE SECONDARY ENDPOINT(S)

The analyses of the secondary endpoints will be performed on the modified ITT data set. Unless otherwise stated, two-tailed nominal p values will be reported.

##### Analysis of mean VR at the end of week 1

In dogs, ScNS reduces ventricular rate during AF. The mean VR was  $149 \pm 36$  bpm after the induction of AF. The VR significantly decreased to  $84 \pm 16$  bpm ( $p=0.011$ ) at the final week of ScNS. The same device that produces AF burden will also generate VR. First, we will summarize the proportion of patients who are AF-free at the end of week 1. Fisher's exact test will be performed to test if the proportions of AF-free patients are the same between the two treatment arms at a two-sided significance level of

0.025. Second, we will summarize the mean VRs using mean and standard deviation by time and by randomization group among the patients who experience AF.

We will classify patients into 3 groups based on the week 1 average VR: patients who do not experience AF as category 1, patients who experience AF with VR  $\leq$  110 bpm as category 2, and patients who experience AF with VR  $>$  110 bpm as category 3. Fisher's exact test will be performed to test if the distribution of the three categories are the same between the two treatment arms and the nominal p-value will be reported.

We will categorize average VR at other time points into three groups as described above, and analyze repeated average VR using ordinal repeated measure analysis with patient as the blocking variable, week and group as well as their interaction as independent variables. Proportional odds assumption will be checked.

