### 9.3 POPULATIONS FOR ANALYSES

1. Safety set: the set of patients who have undergone surgery to insert the subcutaneous lead
2. modified intention-to-treat set: the set of patients who have either the subcutaneous nerve stimulation or the sham stimulation performed AND have baseline average AF burden AND at least the first week's post-stimulation average AF burden.

Our sensitivity analysis on the modified intention-to-treat set will be using the safety set: we will assume 0 reduction in AF burden for patients missing either the baseline or the first week post-baseline AF burden.

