### **Analysis of SKNA and QOL**

Subcutaneous nerve stimulation achieves its effects through neuromodulation, resulting in reduced sympathetic nerve activity. A non-invasive method to measure sympathetic nerve activity is through the skin sympathetic nerve activity (SKNA) recording. We will record SKNA using two different equipment. The first is ME6000 which makes high fidelity SKNA recordings with 10,000 Hz sampling rate. However, ME6000 is not sufficiently portable for ambulatory recordings. Therefore, we added Bittium Faros recorder for ambulatory recording at 1,000 Hz sampling rate.

The quality of life (QOL) is measured using the standard questionnaire to assess the overall effects of treatment on the study subjects.

SKNA recorded with ME6000 at rest and during 6-minute walk will be summarized at each time point using mean and standard deviation.

SKNA recorded with Bittium Faros when patients were ambulatory will be summarized at each time point using mean and standard deviation.

Quality of life (AFEQT-AF, EQ-5Q-5L) will be summarized by item and by overall score at the following time points, baseline, 3 week and 3-month visits using mean and standard deviation.

Change in the average values of SKNA (aSKNA) recording at rest on the procedure day from the baseline will be compared between the randomization groups using the Wilcoxon Rank Sum test. Values of aSKNA recording in ambulatory subjects and during 6-minute walk at baseline, 1 week, 2-week, 3 week and 3-month visits will be compared between randomization groups using linear mixed models, with Group, Week and Group-Week interaction as fixed effects, and a random intercept per subject. Week will be coded first as a categorical variable. If aSKNA appear to be linear in time, we may model Week as a continuous fixed effect. Missing at random will be assumed in the above stated linear mixed models. Additionally, the strategy of last-value-carried-forward (LVCF) will be employed to fill in missing data values as an alternative to the missing-at-random assumption and the linear mixed models will be re-

run. The LVCF analysis serves as a sensitivity analysis. Similar analyses will be performed for SKNA during 6-minute walk.

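### QoL, SKNA and Apple Watch comparisons drop any patient with no usable week-1 AF-burden recording, although their data come from other sources

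*Combined protocol and SAP*

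**What the plan says.** Section 9.4.3 opens with one rule for the analysis set: "The analyses of the secondary endpoints will be performed on the modified ITT data set". Section 9.3 defines that set as patients who had active or sham stimulation and who "have baseline average AF burden AND at least the first week's post-stimulation average AF burden". The ventricular-rate, SKNA, QoL and Apple Watch comparisons all stand under 9.4.3, and none is given a different set.

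For SKNA and QoL the plan specifies linear mixed models: "Missing at random will be assumed in the above stated linear mixed models". Last value carried forward is the sensitivity analysis and "will be employed to fill in missing data values as an alternative to the missing-at-random assumption". The QoL "questionnaires will be compared at the following time points, baseline, 3 week and 3 month visits". Resting SKNA is compared on the procedure day. Ambulatory and walk-test SKNA are compared at baseline, weeks 1, 2 and 3 and month 3.

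For patients outside the modified ITT set, 9.3 offers a sensitivity analysis on the safety set: "we will assume 0 reduction in AF burden for patients missing either the baseline or the first week post-baseline AF burden". It gives no rule for any other endpoint.

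**The concern.** The entry condition suits the primary endpoint, which cannot be computed without week-1 AF burden. It does not suit QoL, SKNA or the Apple Watch comparison. Section 8.1 gets SKNA from separate recorders, QoL from questionnaires and the watch data from the watch. QoL is not collected at week 1 at all, and the procedure-day SKNA comparison precedes any week-1 burden.

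Section 7.1 keeps patients in follow-up after stimulation stops. A patient with no week-1 burden can therefore have complete QoL and SKNA records and still be left out.

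Two things are at stake:

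- **Precision.** Observed data from randomised patients are lost in a 30-patient trial.
- **Comparability.** Selection rests on something measured after randomisation, while only one arm is being stimulated. Section 6.3 expects that stimulation may cause tingling or pain, so the chance of having a week-1 recording could differ by arm.

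**Working it through.** **The plan's own figure.** Section 9.2 gives 15 per arm for the primary Wilcoxon comparison, at 80% power, two-sided alpha 0.025 and 70% retention.

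- Effect size: (76.3 − 5)/44.8 = 1.59.
- Simulated power of the exact Wilcoxon test on normal data at that effect: 78% with 9 per arm, 83% with 10. So 10 evaluable per arm are needed.
- 10/0.70 = 14.3, rounded up to 15.

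The stated size reproduces. This point contests the analysis set, not that number.

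**Who is excluded.**

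- *Missing baseline burden.* Section 5.1 makes a burden from at least 7 days of monitoring an entry criterion, so this should be rare.
- *Partly worn week-1 patch.* Section 9.4.2 divides AF time by observed time and sets no minimum wear. The patient stays in.
- *No usable week-1 recording.* The patient is out. This is the practical trigger.
- *No telemetry at week 2, week 3 or month 3.* Nobody is excluded.

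**Which analyses are affected.**

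- *QoL, SKNA and Apple Watch.* Affected, because the data come from other sources.
- *Week-1 ventricular rate and AF-free status.* Essentially unaffected, because 9.4.3 takes them from the same device as AF burden.
- *Repeated ventricular rate.* Later weeks of an excluded patient are lost.
- *Repeated AF-burden models.* These are in 9.4.2, which names no set, so the effect is unclear.
- *Safety.* Unaffected; 9.4.4 uses the safety set.

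**Whether other rules restore the patient.** The mixed models and the carried-forward analysis deal with missing outcome values inside the set. The safety-set imputation covers AF burden only. Covariate adjustment for differential drop-out (9.4.2) adds nobody. None restores the excluded patient's QoL or SKNA.

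**Size.** The documents give neither a rate of missing week-1 telemetry nor an effect size for QoL or SKNA, so both are assumed here. Let k of 30 patients lack week-1 burden but have QoL observed, with losses averaged evenly over the arms.

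- SE ratio = √(30/(30 − k)).
- Power is for a two-sample t-test, two-sided 5%, 1.0 SD difference, n = (30 − k)/2 per arm, df = 28 − k, noncentrality √(n/2).

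| k | n per arm | SE ratio | Power |
|---|---|---|---|
| 0 | 15 | 1.000 | 75% |
| 1 | 14.5 | √(30/29) = 1.017 | 74% |
| 2 | 14 | √(30/28) = 1.035 | 72% |
| 3 | 13.5 | √(30/27) = 1.054 | 70% |
| 9 | 10.5 | √(30/21) = 1.195 | 58% |

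The last row puts the whole 30% planned loss (0.30 × 30 = 9) at week 1 with every QoL record intact. It is a ceiling, not a forecast.

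**The case against.** The strongest reply is that the rule will rarely matter. Telemetry runs throughout stimulation for safety (8.2), any usable part of week 1 keeps the patient in, and most secondary p values are nominal. That stands, and it limits the size of the point. Ambulatory SKNA is also worn at similar times to the telemetry patch, so the two may be missing together and less would be recovered there.

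A reader might infer more than the documents support:

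- *Any missed telemetry week removes a patient.* Only baseline or week 1 can, and in practice only a week 1 with no usable data.
- *Every secondary analysis, including later AF-burden weeks, is cut.* Time-dependent AF burden is listed as a secondary endpoint in 9.1, so this is arguable. But its models are in 9.4.2, where no set is named.
- *Nine patients leave and power falls to 58%.* The 70% in 9.2 is patient retention, not a telemetry failure rate. Patients who leave the study would mostly lack the later questionnaires too, so widening the set would recover little from them.
- *The arms will be unbalanced.* Stopping stimulation does not end follow-up (7.1). Section 7.2 does allow withdrawal of a patient who cannot receive stimulation, so arm-related loss is possible, but no figure shows it.

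What the reply does not supply is a reason for making QoL or SKNA depend on week-1 telemetry.

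**Conclusion.** The point holds for QoL, SKNA and the Apple Watch comparison, and for later weeks of the repeated ventricular-rate model. The plan excludes patients whose data on these endpoints may be complete, on a post-randomisation condition unrelated to the first three, and nothing else in the plan restores them.

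The precision cost is modest: about 2% to 5% on the standard error and 1 to 5 points of power if 1 to 3 of 30 patients are affected. That range rests on an assumed count, an assumed 1.0 SD effect and observed QoL in those patients. Possible bias from arm-related loss cannot be sized from the documents. The primary comparison is not affected.

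**What to change.** In 9.4.3, state that QoL, SKNA, the Apple Watch comparison and the repeated ventricular-rate model are analysed on all randomised patients, as randomised, with at least one post-baseline value of the endpoint concerned. Requiring a post-baseline value avoids admitting baseline-only patients, who add almost nothing to the group-by-week contrasts. Keep the modified ITT set as a supportive analysis.

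In 9.4.2, name the set for the repeated AF-burden models and apply the same rule.

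Report, by arm, how many patients had no usable week-1 recording, so that the reader can judge the selection.

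The cost is a wording change and one extra run of the same models. No new data or visits are needed.

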## 5.2 EXCLUSION CRITERIA

An individual who meets any of the following criteria will be excluded from participation in this study:

- Patients without AF episodes during monitoring period will be excluded from the study and count as screen failure
- Left ventricular ejection fraction <40%
- Heart failure with functional classes III or IV
- Recurrent vasovagal syncope
- Valvular AF (severe mitral regurgitation, mitral stenosis)
- Congenital heart diseases
- Wolff Parkinson-White Syndrome
- Stroke within the past 6 months
- Any history of myocardial infarction
- Malignancies with a life expectancy of < 1 year
- A history of ablation procedures to treat left atrial tachyarrhythmias or other serious comorbidity
- Any history of sustained ventricular tachycardia (VT) defined by (1) > 30 s in duration or (2) < 30 s in duration, but is associated with hemodynamic consequences such as hypotension and syncope.
- Patients with a vagal nerve stimulator
- Active thyrotoxicosis
- Sick sinus syndrome with symptomatic bradycardia
- Heart rate < 50 beats per minute in sinus rhythm on 12-lead ECG
- Systolic blood pressure < 90 mm Hg
- Any experimental medication concomitantly or within 4 weeks of participation in the study
- Subjects with cardiac implantable electronic device (CIED) such as pacemakers and implantable cardioverter-defibrillators (ICDs)
- Pre-existing neuromodulation devices, such as vagal nerve stimulators, spinal cord stimulators and sacral nerve stimulators
- People with a history of allergy to ECG electrodes, adhesive tape, or nylon
- Pregnant women

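### Both ventricular-rate tests read bpm only through a 110 bpm cut, so a moderate slowing, or one that stays on one side of 110, would mostly be missed; add a supportive test on bpm

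*Combined protocol and SAP*

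**What the plan says.** VR during AF is a listed secondary endpoint (1.1, 3 and 9.1). The third secondary hypothesis in 9.1 asks whether its control differs between the groups. Section 9.4.3, under the heading on mean VR at week 1, plans the following:

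- A Fisher test of AF-free proportions at two-sided 0.025.
- A description of the rates: "Second, we will summarize the mean VRs using mean and standard deviation by time and by randomization group among the patients who experience AF".
- Three week-1 categories: AF-free, then "patients who experience AF with VR $\leq$ 110 bpm as category 2, 24 and patients who experience AF with VR $>$ 110 bpm as category" (the quote stops just before the number of the third category, and the 24 inside it is a reference number). Fisher's exact test asks whether the "distribution of the three categories are the same between the two treatment arms and the nominal p-value will be reported".
- For the rest: "We will categorize average VR at other time points into three groups as described above". An ordinal repeated-measures model then takes "week and group as well as their interaction as independent variables".

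No significance level is set for the two three-category analyses: "Unless otherwise stated, two-tailed nominal p values will be reported". No power is stated for VR.

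On availability of the data, 9.4.3 notes: "The same device that produces AF burden will also generate VR". Section 5.2 adds: "Patients without AF episodes during monitoring period will be excluded from the study and count as screen failure".

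Other quantitative endpoints keep their scale. AF burden (9.4.2) and resting aSKNA (9.4.3) are tested as change from baseline. Ambulatory aSKNA and the quality-of-life scores go into linear mixed models.

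**The concern.** VR is measured in bpm, and the only effect the plan cites is a shift in bpm: 149 ± 36 to 84 ± 16 in dogs. Once each patient is reduced to at most 110 or above 110, a fall from 150 to 115, or from 105 to 80, counts as no change. The separate AF-free test already covers category 1, so what the three-category test adds is the rate information, and it sees that only through the cut.

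The canine figures are also an uncertain guide. They come from the final week of stimulation, while the Fisher test is at week 1. The title of the cited canine study refers to persistent AF, whereas this trial enrols paroxysmal AF (5.1). If human rates start mostly on one side of 110, or fall by less, the rate hypothesis can come out null despite a real slowing, and the plan has no test that would tell the two apart.

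**Working it through.** **Evaluable patients.** The plan's own figure in 9.2 is for the primary endpoint. The effect size is (76.3 − 5)/44.8 = 1.59. A t-test at two-sided 0.025 with 80% power needs 8.90 per arm. Dividing by the Wilcoxon efficiency gives 8.90/0.955 = 9.32, so 10. Then 10/0.70 = 14.3, so 15. The stated 15 per arm reproduces, and about 10 per arm are evaluable.

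**Inputs.** From 9.4.3: control 149 (SD 36), treated 84 (SD 16). Half the canine effect is a mean of (149 + 84)/2 = 116.5 and an SD of (36 + 16)/2 = 26. Assumed, because the documents do not give them: human means and SDs, AF-free share, baseline correlation ρ = 0.5, and two-sided 0.05.

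**Share above the cut.** P(VR > 110) = 1 − Φ((110 − mean)/SD).
- Canine control: (110 − 149)/36 = −1.08, giving 86%.
- Full effect: (110 − 84)/16 = 1.63, giving 5%.
- Half effect: (110 − 116.5)/26 = −0.25, giving 60%.

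A mean fall of 32.5 bpm therefore moves the share above 110 only from 86% to 60%.

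**Power by simulation** (2,000 to 3,000 trials per setting; ranges are over repeat runs). There are 10 evaluable per arm and 10% are AF-free in both arms. Wilcoxon and ANCOVA use patients with AF only. The ANCOVA residual SD is SD × √(1 − ρ²).

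| Sham to ScNS, bpm (SD) | Share >110, sham to ScNS | Planned Fisher 2×3 | Wilcoxon on bpm | ANCOVA with baseline |
|---|---|---|---|---|
| 149 (36) to 84 (16) | 86% to 5% | 96-97% | 98% | 99.7% |
| 149 (36) to 116.5 (26) | 86% to 60% | 14-17% | 48-51% | 63-65% |
| 90 to 70 (20) | 16% to 2% | 3-4% | 45-48% | 58-62% |
| 110 to 90 (20) | 50% to 16% | 23% | 48% | 61% |
| 120 to 100 (20) | 69% to 31% | 26% | 47% | 60% |

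At 15 per arm, the half-effect row becomes 24%, 70% and 82%.

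With nobody AF-free and 10 per arm, slowings that stay mainly on one side of 110 give (Fisher / Wilcoxon / ANCOVA):
- 90 to 75, SD 12: 0% / 70% / 84%
- 100 to 80, SD 15: 7% / 77% / 89%
- 150 to 125, SD 20: 4% / 70% / 84%

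Part of the gap is Fisher's conservatism rather than the cut. With no VR effect it rejects about 1-4% of the time at this size, against about 5% for the bpm tests. For 110 to 90 with nobody AF-free, a rank test on the same categories reaches 33%, between Fisher's 19% and 50% on bpm.

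**Unequal AF-free shares.** Section 9.2 also considers treatment suppressing AF by 75% and sham not at all. Read as 75% against an assumed 5% AF-free, only 10 × 0.25 = 2.5 stimulated patients per trial have a VR. Power (Fisher / Wilcoxon / ANCOVA) is then:
- full canine effect: 99.7% / 56% / 64%
- half effect: 92-93% / 15-16% / 21-22%
- 120 to 100, SD 20: 94% / 18% / 25%

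Fisher's power here comes largely from the AF-free category.

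**Selection bias.** Suppose slower-rate patients are likelier to become AF-free (assumed latent correlation 0.5, SD 20). The mean latent value among those still in AF is 1.27 SD when 25% remain and 0.11 SD when 95% remain. The spurious difference is 0.5 × 20 × (1.27 − 0.11) = 11.6, so treated rates look about 12 bpm higher with no true effect. A true 20 bpm fall would appear as about 8. Under no effect, the bpm tests reject about 8% of the time at 10 per arm and 12-14% at 15.

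**The case against.** The strongest objection is that the three categories solve a real problem. VR is undefined without AF, and whether a patient has AF is settled after randomisation. The planned test keeps every evaluable patient; a bpm test does not. If stimulation suppresses AF as 9.2 contemplates, the bpm comparison loses most of its power and can be biased. This stands, and it rules out replacing the planned test.

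Other points also stand in part. The objective is framed as rate control, and the 110 bpm cut cites a rate-control trial, so the categories have a purpose. The planned means by time and group would still display a slowing, although they do not test it. The p-values are nominal and this is one of several secondary hypotheses, so the stakes are modest.

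A reader might infer that the VR analyses lose much of their power in general. The documents do not support that: at the only VR effect they give, the cut costs about 2 points against Wilcoxon. A reader might also infer that neither test uses baseline VR. That is certain only for the week-1 Fisher test. The ordinal model covers unspecified other time points, which may include baseline, and its power was not simulated.

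**Conclusion.** The concern holds in limited form. No planned test uses VR in bpm, and the week-1 Fisher test has no baseline term. Little is lost if the full canine effect appears, because it crosses 110. For half that effect, or a 20 bpm fall from 90-120 bpm, the planned Fisher test has about 3-26% power at 10 evaluable per arm. A Wilcoxon test on bpm has about 45-50%, and baseline adjustment gives about 60-65%.

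These figures assume human rates and SDs that the documents do not give, a correlation of 0.5, two-sided 0.05 and equal AF-free shares. With unequal shares the ordering can reverse. The finding therefore supports adding a bpm analysis. It does not support demoting the three-category test to a display.

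**What to change.** In 9.4.3, keep the AF-free test, the three-category Fisher test and the ordinal model. Then:

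- Pre-specify a supportive test of the third secondary hypothesis: week-1 mean VR in bpm, compared between groups among patients with AF, adjusted for baseline VR from the qualifying recording where available. If baseline VR is not available, use the Wilcoxon rank sum test on week-1 bpm.
- Add a corresponding mixed model on bpm for the other weeks, with group, week and their interaction, and baseline VR where available.
- State whether baseline is one of the time points in the ordinal model.
- State the limits: the bpm comparison is restricted to patients still in AF after randomisation, is not fully randomised, loses power and can be biased if stimulation makes more patients AF-free, and must be read beside the AF-free and three-category results.

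The cost is SAP wording, data extraction and analysis, with no new visits or patients. Baseline VR may be missing or come from another device, because 1.2 and 5.1 accept a clinical ePatch recording up to six months old. The documents do not say that VR during AF can be retrieved from it, so this should be checked before the wording is fixed.
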